5.2 Blinatumomab Administration

Subjects will receive premedication with dexamethasone 20 mg (or equivalent) intravenously 1 hour (+/- 30 minutes) prior to the first dose of blinatumomab of each cycle, prior to a step dose (such as Cycle 1 day 8), or when restarting an infusion after an interruption of 4 or more hours. Blinatumomab will be administered as a continuous IV infusion through a central venous catheter at a constant flow rate using an infusion pump for a 42 day cycle with cycle 1 and a 28 day cycle with cycle 2. Blinatumomab will start with a 7 day infusion at 9mcg/d. If no grade 3 toxicity after 7 days, the dose will be escalated to 28 mcg/d for 7 additional days. If no grade 3 toxicity after 14 days, blinatumomab will be infused at a target dose of at 112mcg/d for 28 days.

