2.2.4 Pharmacodynamics

PD measures included lymphocytes subsets and cytokines. Consistent pharmacodynamic profiles were observed across clinical trials following the cIV regimen. T-cell dynamics: Following blinatumomab cIV infusion, peripheral T-cell counts initially declined within 1 to 2 days to very low levels, a phenomenon described as redistribution from periphery to tissues. After the initial decline, T-cells started to increase and reached baseline levels in about 14 days. Increase of T-cell counts above baseline was found in some patients. There was no difference between the dynamics of CD4+ and CD8+ T cells. A high inter-individual variability was observed in T-cell

baseline levels. The time to return to baseline was variable across patients (10 to 30 days). B-cell Dynamics: B-cell counts in peripheral blood decreased rapidly and become undetectable during treatment at doses $\geq 5 \mu\text{g}/\text{m}^2/\text{day}$ (or $9\mu\text{g}/\text{day}$) in the majority of patients. No recovery of B-cell counts was observed during the drug-free period between treatment cycles. Incomplete depletion of B cells was observed at doses of 0.5 and $1.5 \mu\text{g}/\text{m}^2/\text{day}$. High inter-individual variability was found in baseline B-cell counts.

Cytokine Dynamics: The measured cytokines were TNF- α , IL-2, IL-6, IL-8, IL-10, IL-12, IL-4, and IFN- γ . Transient elevation of cytokines was observed in some patients in the first 2 days following the blinatumomab infusion. The elevated cytokine levels returned to baseline within 24 to 48 hours during the infusion period. In subsequent treatment cycles, cytokines elevation was only observed in few patients with much less intensity. The magnitude of cytokine elevation trended higher at the higher dose (Figure 2-3). The inter-subject variability in cytokine elevation was large. The mean ($\pm\text{SD}$) Cmax values for IL-10, IL-6, IFN- γ , IL-2, and TNF- α at the $60 \mu\text{g}/\text{m}^2/\text{day}$ were $2459\pm2643 \text{ pg/mL}$, $4391\pm15182 \text{ pg/mL}$, $445\pm 1014 \text{ pg/mL}$, $167\pm227 \text{ pg/mL}$, $201\pm373 \text{ pg/mL}$, respectively, in Study MT103-104.

Figure 2-3. Serum Peak Cytokine Concentration (Mean+SD) Following Initiation of Blinatumomab Treatment

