5. TREATMENT PLAN

5.1 Treatment Regimen

This will be an open label single arm phase II study employing a Simon's optimal two stage design to assess efficacy and safety of blinatumomab in indolent NHL. Blinatumomab will be administered as a continuous IV infusion through a central venous catheter for a 42 day cycle. Blinatumomab will start with a 7 day infusion at 9mcg/d. If no dose limiting toxicity (table 6.1)

after 7 days, the dose will be escalated to 28 mcg/d for 7 additional days. If no dose limiting toxicity (table 6.1) after 14 days, blinatumomab will be infused at a target dose of at 112mcg/d for 28 days. The first 5 patients enrolled on study will be admitted for 3 days during each dose escalation as well as the first 3 days of cycle 2 to monitor for cytokine release syndrome as well as neurotoxicity. If no grade 4 toxicities are seen, future patients enrolled on study will begin therapy as an outpatient. Subjects will be restaged after a 6 week treatment free period by PET CT. All subjects without disease progression will receive an additional 4 week cycle starting at the target dose of 112 mcg/d. All subjects will then have an end of treatment PET CT 6 weeks after completion of the second infusion. All subjects with a response will then be followed with a CT every 6 months for the first 2 years and then annually for 5 years or until progression.

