6. DOSING DELAYS/DOSE MODIFICATIONS

6.1 Toxicity Management/ Dosage Adjustments

Table 6-1 Criteria for dosing delays and re-initiation of treatment for toxicity definitely or possibly related to study drug. Based on the Common Terminology Criteria for Adverse Events (CTCAE) version 4.0.

Toxicity	Grade	Action
Cytokine Release Syndrome (CRS)	Grade 3	Withhold blinatumomab until resolved to \leq grade 1, then restart blinatumomab at 9 mcg/day with dexamethasone 8mg TID for three days. Dexamethasone will then be decreased by 25% per day until discontinued. Escalate to 28 mcg/day after 7 days and then to 112 mcg/d after an additional 7 days if the toxicity does not recur.
	Grade 4	Remove from study
Neurologic toxicity	Seizure	Discontinue blinatumomab permanently if more than one seizure occurs despite antiepileptics.
	Grade 3	Withhold blinatumomab until \leq grade 1, (mild), then restart blinatumomab at 9 mcg/day with dexamethasone (or equivalent) 20mg iv within 1 hour of start of retreatment. Dexamethasone will then be decreased by 25% per day until discontinued. Escalate to 28 mcg/day after 7 days and then to 112 mcg/d after an additional 7 days if the toxicity does not recur. If the toxicity occurred at 9 mcg/day, or if the toxicity takes more than 7 days to resolve, discontinue blinatumomab permanently
	Grade 4	Remove from study
Other clinically relevant adverse reactions	Grade 3	Withhold blinatumomab until \leq grade 1 (mild), then restart blinatumomab at 9 mcg/day. Escalate to 28 mcg/day after 7 days and then to 112 mcg/d after an additional 7 days if the toxicity does not recur. If the toxicity occurred at 9 mcg/day, or if the toxicity takes more than 7 days to resolve, discontinue blinatumomab permanently
	Grade 4	Remove from study

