8.1.8 Administration

Subjects will receive premedication with dexamethasone 20 mg (or equivalent) intravenously 1 hour prior to the first dose of blinatumomab of each cycle, prior to a step dose (such as Cycle 1 day 8), or when restarting an infusion after an interruption of 4 or more hours. Blinatumomab will be administered as a continuous IV infusion through a central venous catheter at a constant flow rate using an infusion pump for a 42 day cycle. Blinatumomab will start with a 7 day infusion at 9mcg/d. If no dose limiting toxicity (table 6.1) after 7 days, the dose will be escalated to 28 mcg/d for 7 additional days. If no dose limiting toxicity (table 6.1) after 14 days, blinatumomab will be infused at a target dose of at 112mcg/d for 28 days.

Blinatumomab solution for infusion may be administered using IV bags and infusion lines made of polyolefin/polyethylene, ethylene vinyl acetate (EVA), or PVC non-DEHP. Infusion lines with an in-line 0.2 μ m filter should be used.

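### Section 5.2 bars dose escalation after any grade 3 toxicity, does not exempt the expected lymphopenia, and conflicts with the gate in Sections 5.1 and 8.1.8

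*Combined protocol and SAP*

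**What the plan says.** The escalation condition appears in three places, in two forms.

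- **Section 5.2**, step to 28 mcg/day: "If no grade 3 toxicity after 7 days, the dose will be escalated to 28 mcg/d for 7 additional days". Step to 112 mcg/day: "If no grade 3 toxicity after 14 days, blinatumomab will be infused at a target dose". Nothing is said about relatedness, clinical relevance or laboratory findings, or about what to do with a subject who does not meet the condition.
- **Section 5.1**, step to 112 mcg/day: "If no dose limiting toxicity (table 6.1) after 14 days, blinatumomab will be infused at a target dose". **Section 8.1.8**, step to 28 mcg/day: "If no dose limiting toxicity (table 6.1) after 7 days, the dose will be escalated to 28 mcg/d for 7 additional days". Each section uses the same form for its other step.

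Table 6-1 (Section 6.1) does not define dose-limiting toxicity. It covers events judged definitely or possibly drug-related. Beyond cytokine release syndrome and neurologic toxicity it has one residual row, headed "Other clinically relevant adverse reactions". In that row grade 3 means withhold and restart at 9 mcg/day, with this limit: "If the toxicity occurred at 9 mcg/day, or if the toxicity takes more than 7 days to resolve, discontinue blinatumomab permanently". Grade 4 means removal from study. Lymphopenia is not named in any of these places.

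Section 2.2.4 describes lymphocyte depletion as the drug's pharmacodynamic effect: "peripheral T-cell counts initially declined within 1 to 2 days to very low levels". T cells regain baseline in about 14 days (range 10 to 30). B cells become undetectable in most patients from 9 mcg/day upward.

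**The concern.** The same laboratory value can lead to three different treatment paths. Under Section 5.2 as written, the subject may not escalate. Under the residual row of Table 6-1, the subject stops permanently or is removed. If the investigator judges the finding not clinically relevant, the subject escalates under Sections 5.1 and 8.1.8, but in breach of Section 5.2. The third path is probably what was intended, yet no text says so.

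The trial is meant to test a target dose of 112 mcg/day. A rule that withholds that dose, or ends treatment, because of the drug's own expected effect works against this aim. It also bears on the primary endpoint. Sections 11.2 and 13.3.2 count a subject as response-evaluable only after at least one cycle and re-evaluation, or on progression. A subject stopped for lymphopenia before a full cycle and without progression therefore drops out of the response analysis.

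**Working it through.** **The plan's own figures.** Section 13.2 uses at least 6 of 13 responses, then at least 15 of 28. The exact two-stage probability of success is the sum over x = 6 to 13 of P(X1 = x) × P(X2 ≥ 15 − x), with X1 ~ Bin(13, p) and X2 ~ Bin(15, p). At p = 0.40 it is 0.0930 (stated 0.093). At p = 0.65 it is 0.9035 (stated 0.904). Early stopping, P(X1 ≤ 5), is 0.574 and 0.046 (stated 0.57 and 0.05). All reproduce. The point here concerns who receives the target dose and who is analysed, not these figures.

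**Timing of the gates against the expected effect (Section 2.2.4).**

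| Event | Day |
|---|---|
| T cells fall to very low levels | 1 to 2 |
| Gate to 28 mcg/day | 7 |
| Earliest stated T-cell return to baseline | 10 |
| Gate to 112 mcg/day; typical T-cell return | 14 |
| Latest stated T-cell return | 30 |

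The first gate comes before the earliest stated return (7 < 10). The second lies inside the range (10 ≤ 14 ≤ 30). The finding will be seen: a CBC with differential is weekly (Section 10.2.1), and B and T cells are counted on day 8 of cycle 1 (Section 10.4, item 8 of the visit schedule). Section 2.2.4 gives no absolute lymphocyte counts, so it shows a foreseeable trigger, not that grade 3 is reached by day 7.

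**How often grade 3 or higher was reported (Table 2-4, NHL column).** 60/95 = 63.2%, exact 95% CI 52.6 to 72.8%. Three limits apply:

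- Doses were mixed, up to 90 mcg/m²/day.
- The whole treatment period counts.
- 76 of the 95 patients (76/95 = 80%) came from MT103-104, where all laboratory changes had to be reported.

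The figure is best read as an upper guide, not as a week-1 rate. Serious lymphopenia was reported in 42/95 = 44.2% (Table 2-5). MT103-104 required grade 4 laboratory abnormalities to be reported as serious, so some of these were probably grade 4, but the documents do not split the grades.

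**What each text does with isolated grade 3 lymphopenia arising at 9 mcg/day.**

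| Text followed | Result |
|---|---|
| Section 5.2, literally | No escalation; next step not stated |
| Table 6-1 residual row, judged clinically relevant | Permanent stop |
| Same row at grade 4 | Removal from study |
| Sections 5.1 and 8.1.8, judged not clinically relevant | Escalation, contrary to Section 5.2 |

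**Effect on the response analysis.** Each subject stopped before a full cycle without progression takes 1/28 = 3.6% off the planned evaluable number, or 1/13 = 7.7% if this happens in stage 1, unless replaced.

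**The case against.** The best reply is that the plan already deals with this. Two of the three statements of the gate point to Table 6-1, and that table is limited to drug-related events and, in its residual row, to clinically relevant ones. Section 2.2.6 treats laboratory changes reported regardless of clinical relevance as a feature of the earlier phase 1 study. Section 2.2.4 presents the T-cell fall as redistribution to tissues, not as toxicity. A sensible investigator could set isolated lymphopenia aside without an amendment. This stands for Sections 5.1 and 8.1.8. It does not help with Section 5.2, which has no such filter, and it rests on a term that nothing defines.

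The reply is also right that the frequency at 9 mcg/day is unknown.

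Three stronger readings are tempting, and the documents do not support them.

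- *Affected subjects would spend the cycle at 9 mcg/day.* No text says so. Section 5.2 is silent on the next step, and Table 6-1, where it applies, stops treatment. Counts of subjects held at that dose would rest on assumed rates. The responses in Table 2-6 (0/7 at 5 and 24/35 at 60 mcg/m²/day) therefore cannot be read as the consequence. They are also non-randomised, cover all NHL types and are grouped by the maximal dose reached.
- *Power would fall in proportion to the subjects affected.* That requires counting them as non-responders in the analysis. Those stopped before a full cycle without progression are not counted at all under Sections 11.2 and 13.3.2.
- *Earlier studies commonly treated through lymphopenia.* Of the 60 patients, at most 34 stopped for any adverse event (Table 2-2), which leaves at least 60 − 34 = 26. But 23 patients had interruptions, so the guaranteed minimum with neither is 60 − 34 − 23 = 3.

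**Conclusion.** The concern holds as a conflict between sections that should be removed by amendment. Section 5.2 makes any grade 3 toxicity a bar to both step-ups, Sections 5.1 and 8.1.8 use a different gate, and no text exempts an effect that the protocol itself expects within days of starting. Following Section 5.2 as written would deny the target dose for lymphopenia. Applying the residual row of Table 6-1 would end treatment and could take the subject out of the response-evaluable set.

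The number affected cannot be stated. The only frequency available is 60/95 (63.2%), pooled over doses and time under mandatory laboratory reporting in most patients. The conclusion assumes that Section 5.2 is read as grade 3 or higher, and that some subjects reach that grade by day 7 or day 14. The pharmacodynamic description makes this likely but does not prove it. The Simon design and its stated error rates are unaffected.

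**What to change.** 1. Use one gate in Sections 5.1, 5.2 and 8.1.8: *no grade 3 or higher toxicity requiring action under Table 6-1*.
2. Add to Table 6-1: *Isolated grade 3 or 4 lymphopenia (including lymphocyte count decreased, and leukopenia due only to it) without associated infection is not a clinically relevant reaction and does not require holding, stopping or withholding escalation.* The related terms are needed because Table 2-4 lists lymphocyte count decreased (4/95) and leukopenia (17/95) separately from lymphopenia.

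All other toxicity stays under the current rows of Table 6-1. Other common laboratory findings, such as raised C-reactive protein (17/95 at grade 3 or higher) or hyperglycaemia (10/95), would then block escalation only if judged clinically relevant. That judgement remains with the investigator.

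The cost is one aligned phrase in three sections and one line in the table, with no added visits, tests or subjects. The downside is slightly less caution about infection in lymphopenic subjects. It is a real one: of the 7 deaths considered possibly related in Section 2.2.6, 3 + 1 + 1 + 1 = 6 were infections (sepsis, pneumocystis pneumonia, invasive fungal infection, candidiasis). The exemption therefore ends when infection is present, and the weekly CBC and clinical review already scheduled in Section 10.2 provide the monitoring.

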5.3 General Concomitant Medication and Supportive Care Guidelines

Patients will be instructed not to take any additional medications (including over-the-counter products) during the course of the study without prior consultation with the investigator. At each visit, the investigator will ask the patient about any new medications he/she is or has taken after the start of the study drug.

All Concomitant medications/Significant non-drug therapies taken \leq 30 days prior to start and after start of study drug, including physical therapy and blood transfusions, should be recorded.

The following restrictions apply during the entire duration of the study:

- No other investigational therapy should be given to patients.
- No anticancer agents other than the study medication should be given to patients. If such agents are required for a patient then the patient must first be withdrawn from the study.
- Growth factors (e.g.G-CSF, GM-CSF, erythropoietin, platelets growth factors etc.) may be used at the discretion of the treating investigator.
- No chronic treatment with systemic steroids at >20 mg/day of prednisone, or equivalent, or another immunosuppressive agents. Topical or inhaled

corticosteroids are allowed. Musculoskeletal injections of steroids are allowed.

- No formal drug interaction studies have been conducted with blinatumomab. Initiation of blinatumomab treatment causes transient release of cytokines that may suppress CYP450 enzymes. The highest drug drug interaction risk is during the first 9 days of the cycle and in patients who are receiving concomitant CYP450 substrates, particularly those with a narrow therapeutic index. In these patients, monitor for toxicity (eg, warfarin) or drug concentrations (eg, cyclosporine).

5.4 Criteria for Taking a Participant Off Protocol Therapy

Duration of therapy will depend on individual response, evidence of disease progression and tolerance. In the absence of treatment delays due to adverse event(s), treatment may continue for 2 cycles or until one of the following criteria applies:

- Disease progression
- Intercurrent illness that prevents further administration of treatment
- Unacceptable adverse event(s)
- Participant demonstrates an inability or unwillingness to comply with the oral medication regimen and/or documentation requirements
- Participant decides to withdraw from the protocol therapy
- General or specific changes in the participant's condition render the participant unacceptable for further treatment in the judgment of the treating investigator

Participants will be removed from the protocol therapy when any of these criteria apply. The reason for removal from protocol therapy, and the date the participant was removed, must be documented in the case report form (CRF). Alternative care options will be discussed with the participant.

A QACT Treatment Ended/Off Study Form will be filled out when a participant is removed from protocol therapy. This form can be found on the QACT website or obtained from the QACT registration staff.

In the event of unusual or life-threatening complications, treating investigators must immediately notify the Overall PI, [name] M.D., Ph.D. at [contact].

5.5 Duration of Follow Up

Participants removed from study due to criteria in section 5.4 will be followed for survival for 5 years or until death. . Participants removed from protocol therapy for unacceptable adverse event(s) will be followed monthly until resolution or stabilization of the adverse event.

5.6 Criteria for Taking a Participant Off Study

Participants will be removed from study when any of the following criteria apply:

- Lost to follow-up
- Withdrawal of consent for data submission
- Death

The reason for taking a participant off study, and the date the participant was removed, must be documented in the case report form (CRF).

For Centralized Subject Registrations, the research team submits a completed Off Treatment/Off Study form to ODQ when a participant comes off study. This form can be found on the ODQ website or obtained from the ODQ registration staff.

For Decentralized Subject Registrations, the research team updates the relevant Off Treatment/Off Study information in OnCore.

6. DOSING DELAYS/DOSE MODIFICATIONS

6.1 Toxicity Management/ Dosage Adjustments

Table 6-1 Criteria for dosing delays and re-initiation of treatment for toxicity definitely or possibly related to study drug. Based on the Common Terminology Criteria for Adverse Events (CTCAE) version 4.0.

Toxicity	Grade	Action
Cytokine Release Syndrome (CRS)	Grade 3	Withhold blinatumomab until resolved to \leq grade 1, then restart blinatumomab at 9 mcg/day with dexamethasone 8mg TID for three days. Dexamethasone will then be decreased by 25% per day until discontinued. Escalate to 28 mcg/day after 7 days and then to 112 mcg/d after an additional 7 days if the toxicity does not recur.
	Grade 4	Remove from study
Neurologic toxicity	Seizure	Discontinue blinatumomab permanently if more than one seizure occurs despite antiepileptics.
	Grade 3	Withhold blinatumomab until \leq grade 1, (mild), then restart blinatumomab at 9 mcg/day with dexamethasone (or equivalent) 20mg iv within 1 hour of start of retreatment. Dexamethasone will then be decreased by 25% per day until discontinued. Escalate to 28 mcg/day after 7 days and then to 112 mcg/d after an additional 7 days if the toxicity does not recur. If the toxicity occurred at 9 mcg/day, or if the toxicity takes more than 7 days to resolve, discontinue blinatumomab permanently
	Grade 4	Remove from study
Other clinically relevant adverse reactions	Grade 3	Withhold blinatumomab until \leq grade 1 (mild), then restart blinatumomab at 9 mcg/day. Escalate to 28 mcg/day after 7 days and then to 112 mcg/d after an additional 7 days if the toxicity does not recur. If the toxicity occurred at 9 mcg/day, or if the toxicity takes more than 7 days to resolve, discontinue blinatumomab permanently
	Grade 4	Remove from study

7. ADVERSE EVENTS: LIST AND REPORTING REQUIREMENTS

Adverse event (AE) monitoring and reporting is a routine part of every clinical trial. The following list of reported and/or potential AEs (Section 7.1) and the characteristics of an observed AE (Section 7.2) will determine whether the event requires expedited reporting **in addition** to routine reporting.

7.1 Expected Toxicities

7.1.1 Cytokine Release Syndrome

Cytokine Release Syndrome (CRS), which may be life-threatening or fatal, occurred in patients receiving blinatumomab.

Infusion reactions have occurred with the blinatumomab infusion and may be clinically indistinguishable from manifestations of CRS.

Serious adverse events that may be associated with CRS included pyrexia, headache, nausea, asthenia, hypotension, increased alanine aminotransferase, increased aspartate aminotransferase, and increased total bilirubin; these events infrequently led to blinatumomab discontinuation. Life-threatening or fatal CRS was infrequently reported in patients receiving blinatumomab. In some cases, disseminated intravascular coagulation (DIC), capillary leak syndrome (CLS), and hemophagocytic lymphohistiocytosis/macrophage activation syndrome (HLH/MAS) have been reported in the setting of CRS.

Subjects will be closely monitored for signs or symptoms of these events. Management of these events will require either temporary interruption or discontinuation of blinatumomab (see table 6-1).

